There will be a total of 5 visits for this pilot study. The first two visits will consist of the initial clinical assessment and optional imaging split over 2 days (no specific sequence or preset time interval). At visit 1 or 2, participants will be instructed to wear physical activity and sleep trackers (ActivPal, which is a sensor that will be put on the upper leg and a ring called Oura ring, which will be worn at a finger) for approximately 1 week prior to visit 3. Participants will also wear a continuous glucose monitor during the same time. After the participants complete the approximate 1 week of physical activity, sleep and glucose monitoring they will return for visit 3, where a limited repeat clinical test battery will be administered. At visit 3 the participant will also be instructed to start the approximately 30-day supplementation of KE drink as well as to wear the sleep tracking ring throughout their time taking the supplement. Participants who are willing and eligible to take part in the optional single-day sub-study will complete the optional sub-study at visit 3, where they will still get the first dose of the KE drink in lab. See page 19 of protocol for more information on the optional sub-study. The physical activity tracker and the continuous glucose monitor will also be worn during the last week of the KE supplementation period. At the end of the approximately 30-day KE supplementation, the participants will return for visits 4 (repeat clinical assessment) and 5 (repeat optional imaging) again split over 2 days. There is no preset sequence which assessment (clinical or imaging) comes first. Blood tests will be collected for assessments of genetic variables (e.g. ApoE). Blood and/or urine assessments will also be used for metabolomics, inflammatory markers, and/or screening measures. Blood continuous glucose data will be collected blinded to the participant, except for the first week of taking the ketone ester as this

information is needed for safety monitoring purposes. Participants will also take readings of their glucose and ketone body levels using a Keto-Mojo device (see Table 2 for more information).

Labs to be performed:

- CBC w/ Diff
- CMP w/ eGFR
- High-sensitivity CRP
- Hemoglobin A1c
- RBC Magnesium
- Phosphorus
- Albumin
- TSH
- T4
- Reverse T3
- Lipid Panel
- Urinalysis
- Beta-2 Microglobulin
- Homocysteine
- Vit D (25-hydroxyvitamin D)
- Folate
- Uric acid serum

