Finger Tapping ²	X			X (optional)		X X	
Electronic Gait	Х			X (optional)		Х	
Mat/sensored							
walk ²							
(optional for							
PDD/LBD/MCI							
patients)	_						
Beck Depression	Х			Х		Х	
Inventory II scale							
Spielberger Trait Anxiety Scale	Х			Х		Х	

Sleepiness scales	Х				Х	
MoCa, PDCRS (limited cognition)	Х		X (optional)		X	
Cognitive test battery**	Х		X (optional)		X	
PCFRS functional scale	Х				X	
Clinical Dementia Rating (CDR) Scale****	Х				X	
Quality of life scale PDQ-39	Х				X	
Adverse event assessment	Х		Х		X	
Phone Call / email drug monitoring				Х		
Drug accountability			Х		Х	
Pregnancy test in women of childbearing potential		X (within 48 hours of PET)	X			X (within 48 hours of PET)

Note

¹: Fasting in morning

²: Dopaminergic off state in PD

³: Participants will take 12.5g BID for day 1 of intervention, 12.5g TID for days 2 through 7 and increase dose to 25g on day 8 of intervention

⁴: Visit 3 will have optional motor and cognitive testing for individuals who have more than 2 months between their baseline clinical assessment and pre-intervention clinical assessment. For those individuals who do not have to complete motor testing, they will not be required to withhold dopaminergic medication. For individuals taking part in the optional sub-study during the pre-intervention visit, they will still be required to withhold their medication and fast the morning of the visit.

*Visits 1-2 and 4-5. There is no pre-set sequence which assessment (clinical or imaging) comes first. There may be a time interval of up to two months between Visits 1 and Visits 3, depending on scheduling

**Portions of cognitive test battery will be optional for LBD/PDD/MCI participants in anticipation of fatigue

Keto-mojo usage will be optional if it is deemed too difficult for participant to administer by themselves. It will be required prior to post-intervention imaging and clinical visit (V4/5), but may be performed by research staff as needed *Clinical Dementia Rating Scale will only be completed by LBD/PDD/MCI subjects

Details of the neuropsychological test battery is shown in Table 3.

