days (a total of 2.1 L). Anthropomorphic measurements, plus fasting blood and urine analyses were made weekly. It was found that elevating blood β HB concentrations from 0.1 to 4.1 (±1.1) mM three times a day for 28 days had no effect on body weights or composition, fasting blood glucose, cholesterol, triglyceride or electrolyte concentrations, nor blood gases or kidney function, which were invariably normal ³⁶. In addition, a 28-day study in patients with type 2 diabetes also on 26.8 g t.i.d. po found that all participants had >90% adherence, defined as consumption of at least 76 of the maximum 84 KE drinks. Thus, the KE drink was well-tolerated. Adverse symptoms were self-recorded by participants following each of their drinks and were ranked as 'mild', 'moderate' or 'severe'. Overall occurrence of adverse symptoms is expressed relative to the total number, 1,588, of drinks consumed throughout the entire study; mild nausea (5/1,588 = 0.3%), mild headache (5/1,588 = 0.3%) and mild gastric discomfort (9/1,588 = 0.5%) were the only reported symptoms ³⁷. Mild nausea was reported following 6 of the 2,016 drinks consumed in the 28-day healthy control study ³⁶.

Research staff will administer the first dose of KE drink at Visit 3 in lab to monitor subjects (day 1), and then subjects will be sent home and asked to take a second dose of KE drink with their next meal (day 1). For days 2 through 7, participants will take 12.5g (25mL) TID, and on day 8, the dose will be increased to 25g (50mL) TID as tolerated. KE dose will be titrated down to a tolerated level if necessary. Participants will be asked to take the KE doses with meals to decrease side-effects of hypoglycemia. If participants are experiencing feelings of low glucose levels and/or a blood glucose reading of <65mg/dL (via unblinded continuous glucose monitor and/or KetoMojo reading), participants will be asked to skip the KE dose and wait until their next meal to take a dose. Glucose and ketone body levels will be monitored for the first ~7days using Keto-Mojo (optional) to decrease chances of hypoglycemia, as well as taken weekly for the duration of the KE intervention (optional). Glucose and ketone body levels will also be monitored prior to the post-intervention clinical testing and imaging. Staff will ask participants to limit their alcohol consumption to a maximum of one glass per day and take the final daily dose at least 4 hours prior to sleep.

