Sixty minutes after consumption of KE, or 30 minutes after completion of the Modified Curtis Protocol, participants will undergo repeat testing including the MDS-UPDRS_{III}, TUG, FTT, GSRS, a side effect assessment, and serum glucose/ketone body lab testing via Keto-Mojo. This same testing plus the Mini-ACE will also recur after 120 minutes (2 hour) and 240 minutes (4 hour) from the time of time the KE drink was finished. After the 4-hour testing is complete,

participants will be allowed to take their held medications, can resume their normal diet, and will be dismissed for the day.

Our study team will follow up with participants by phone in the 48 hours following the in-person Study Visit to ask about potential side effects and to repeat the GSRS as well as ask the closing question which is a Likert scale survey question regarding likeliness that the participant feels they could repeat this protocol on a daily basis. Once the follow-up phone call ends, the sub-study will be complete.

Visit 3 in the original study document consists of psychiatric clinical testing as well as optional motor and cognitive testing. Participants who opt to take part in this sub-study will be exempt from completing the original planned assessments for this day as per the Schedule of Activities (SoA) (besides the Beck Depression Inventory II and Spielberger Trait Anxiety scale which will be completed by all participants at visit 3). The administration of the ketone product and blood lab testing for this visit would be per the sub-study protocol as opposed to the original protocol. Participants would still receive the sleep tracking ring, pregnancy testing (if applicable), and drug accountability before starting the original intervention protocol.

For individuals who cannot tolerate the Curtis protocol intervention, study staff will send home the participants without the KetoneAid supplement and call them within 48 hours to monitor any side effects from testing. Participants may be asked to come back in to the lab to take the KE supplement without any additional testing to assess tolerability of the ketone ester drink alone.

Modified Curtis Protocol Components:

Ketone Ester:

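### In sub-study participants who go on to home dosing, the phone GSRS, side-effect report and Likert question are usually confounded by home KE drinks

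*Combined protocol and SAP*

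**What the plan says.** The sub-study takes place at Visit 3. The Methods text under Overall strategy says of sub-study participants that this is "where they will still get the first dose of the KE drink in lab", and Table 2 confirms that the first dose may be taken during the sub-study.

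For what follows, the KE intervention section says "subjects will be sent home and asked to take a second dose of KE drink with their next meal (day 1"; and then "For days 2 through 7, participants will take 12.5g (25mL) TID". Note 3 to Table 2 agrees: "Participants will take 12.5g BID for day 1 of intervention, 12.5g TID for days 2 through 7". The sub-study text states no delay or washout. It has participants receive "drug accountability before starting the original intervention protocol" and lets them resume their usual diet after the 4-hour tests.

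The call may come at any point in the window: "Our study team will follow up with participants by phone in the 48 hours following the in-person Study Visit to ask about potential side effects". Staff are also "to repeat the GSRS as well as ask the closing question which is a Likert scale survey question", which concerns whether the participant could repeat the protocol every day. The Likert question is scheduled nowhere else.

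Participants who cannot tolerate the session are sent home without the supplement and are also called within 48 hours about side effects.

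In the lab, the sub-study Schedule of Activities collects the GSRS at baseline, 1, 2 and 4 hours and side effects at 1, 2 and 4 hours. The Aim 2 outcome is the MDS-UPDRS III change at 1 hour. The GSRS and adverse event report are listed as additional measures.

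**The concern.** Aim 2 of the sub-study is tolerability of a single-day regimen. In a participant who continues, a stomach complaint reported at the call could come from the session or from KE drinks taken at home since, without coffee or exercise. Symptom type does not separate the two. The main protocol's KE risk list and the sub-study's risk list for the coffee supplement both include nausea, gastric or abdominal discomfort, distention or bloating, and diarrhea.

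The plan does not ask for the number of home drinks taken before the call or for symptom onset times, and it gives no rule for attributing symptoms. The amount of home KE behind each answer therefore depends on when staff happen to phone. It also differs by group: those who tolerated the session have usually had home drinks, and those who did not have had none.

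The sub-study aims for 10 participants, so each one is 1/10 = 10 percentage points of any symptom rate. A few late symptoms of unclear origin could change the tolerability description. The Likert answer is the most exposed item because it has no counterpart in the lab.

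**Working it through.** **Plan's own figures.** The documents give no figure for drinks taken before the call. The sub-study's one computed figure, a sample size of 10, does reproduce. An exact paired t-test with a change of 0.5 mmol, an SD of 0.5 mmol read as the SD of the change, and two-sided alpha 0.05 has power 0.748 at n = 9 and 0.803 at n = 10. Nothing below depends on it.

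**Inputs from the documents.**
- Home drinks on day 1: one (two doses that day, the first in the lab).
- Home drinks on days 2 to 7: three per day, 12.5 g each.
- Call: from dismissal to 48 hours after the visit.
- Length of the session: baseline tests 30 to 60 minutes, then 30 minutes from coffee to KE, then 240 minutes from KE to the last tests. That is 0.5 to 1 h + 0.5 h + 4 h = 5 to 5.5 h, plus the time for the last tests.

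**Assumptions (no clock times are given).** A morning arrival implies dismissal around 13:00 to 14:30. Meals are at 08:00, 12:30 and 18:00, the next meal after dismissal is the 18:00 one, and every scheduled drink is taken.

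**Count.** Home drinks are the scheduled meals between dismissal and the call, and home KE is 12.5 g × drinks. Dismissal at 13:00 and at 14:30 gives the same result:

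| Call after dismissal | Home drinks | Home KE |
|---|---|---|
| 3 h | 0 | 0 g |
| 6 to 12 h | 1 | 12.5 g |
| 24 h | 1 + 2 = 3 | 37.5 g |
| 36 h | 1 + 3 = 4 | 50 g |
| 48 h | 1 + 3 + 2 = 6 | 75 g |

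At the end of the window, home KE is up to 75 / 12.5 = 6 times the dose under test. A participant who has fasted all morning may eat soon after leaving. The first home drink then comes earlier and the drink-free interval shrinks. The counts from 6 h onward do not change, because day 1 has only one home drink.

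**Which data are exposed.**

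| Measure | Home KE beforehand? |
|---|---|
| MDS-UPDRS III at 1 h (Aim 2 outcome) | No |
| GSRS and side effects in the lab, to 4 h | No |
| Phone GSRS and side-effect report, participant continues | Usually, 0 to about 6 drinks |
| Likert question, participant continues | Usually, with no lab version |
| Call to a participant sent home without KE | No |

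The last row assumes that any return visit to try KE alone comes after the call. The documents do not say when that visit would take place.

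**The case against.** A reader might infer that the call cannot measure tolerability of the single-day protocol at all, or that home-dosing symptoms will be credited to that protocol. The documents support neither reading.

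- Most of the tolerability data are collected in the lab before any home drink, and the formal outcome is fixed at 1 hour. No test of the phone GSRS is specified.
- A same-day call before the next meal is allowed and would be free of home dosing.
- Some effects listed for exercise or caffeine, such as muscle soreness, muscle strain, palpitations and anxiety, are not on the KE risk list. The call can still inform on these.
- The plan is silent on attribution. It says that adverse events are classified by standard criteria and discussed monthly. The gap is a missing rule, not a planned misattribution.
- KE is part of the regimen, so some experience of repeated KE may be relevant to whether a person could repeat it daily. That home drinks change the answer is plausible but not shown.
- Six drinks is an upper bound. The main protocol allows skipped and reduced doses, which would lower the count. The count also does not estimate bias in any outcome.
- Ending tolerability assessment at 4 hours would lose delayed effects, which a 48-hour call is well placed to catch.

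All of this stands, and it narrows the point. It does not remove it. For participants who continue, nearly every call in the window follows at least one home drink. Gut symptoms are where the risk lists overlap most, and the Likert question is asked only then.

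**Conclusion.** The point holds for participants who tolerate the session and continue. Their phone GSRS, side-effect report and Likert answer usually combine the single-day regimen with 0 to about 6 home KE drinks (up to about 75 g), and the plan has no means of separating them. The upper figure rests on early-afternoon dismissal, usual meal times, full adherence and a call at the end of the window. That home drinks usually precede the call rests only on the dosing schedule and the absence of a stated delay.

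The consequence is limited. It affects supplementary tolerability measures in an optional sub-study of 10. It touches neither formal outcome, no planned test and no sample size. It merits a change because GSRS and adverse events are named as tolerability measures and the correction costs very little.

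**What to change.** In the sub-study Schedule of Activities and the text on the follow-up call:

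1. Name the 4-hour GSRS and side-effect report as the uncontaminated gastrointestinal tolerability result.
2. Ask the Likert question at 4 hours as well as at the call.
3. Keep the 48-hour call with its GSRS. At the call, record the number of home KE drinks taken and the onset of each symptom relative to the second KE drink.
4. Report symptoms that began before the second drink as sub-study effects. Tabulate later ones separately by number of drinks taken, described as not attributable to the single-day protocol alone.

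The cost is two extra fields on the phone form, one repeated question and a sentence or two of text. Late gastrointestinal effects remain descriptive. No change to dosing is proposed.
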